There will be a total of 4 testing visits (visits 1, 2 3 and 4 as described above) prior to starting the study, after which, subjects will receive treatment for visits 5-16). After completion of treatment, the subjects will then be re-tested on the baseline assessments and resting state MRI (Post-intervention Visits 17, 18, 19 and 20the total amount of visits for TBI subjects will be 20.). Healthy Control Subjects will have a total of three testing visits (1-3) only.

The subjects with TBI will then be randomly assigned to one of two groups, each consisting of 10 subjects. Subjects will be randomized by a simple randomization method. They will have a 50/50 chance of being in either group by flipping of a coin. Randomization will be carried out by the PI. Subjects and study personnel performing assessments and data analysis will be blind to group assignment. Only the PI will be unblinded.

The experimental group will receive active tDCS for 20 minutes and computerized cognitive training twice a week for 30-45 minutes for 6 weeks as described below. The control group will receive sham-tDCS 20 minutes and computerized cognitive training for 30-45 minutes twice a week for 6 weeks (12 training sessions). The sham group will not receive real tDCS after completion of the study.

In addition, we will conduct a qualitative interview with each of the subjects. Giorgi's phenomenology (Giorgi 1985; Kleiman 2004) is the method that will be used to describe the experiences of persons undergoing tDCS for treatment of TBI. In-person audio-taped interviews will be conducted at the completion visit by an experienced qualitative interviewer and immediately transcribed verbatim. Interviews are expected to range from 30 minutes to 1 hour. Each of the subjects will be asked the open-ended question, "Please tell me about your experience undergoing tDCS for the treatment of traumatic brain injury." Probes included the following questions: "What was the experience like for you? What should we continue to do and what should we change to make the experience better for patients?" Themes will be derived using the constant comparative method (Sandelowski 1995; Thorne 2000).

II. CHARACTERSTICS OF THE RESEARCH POPULATION

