- 7. Vulnerable Subjects.** Although TBI patients have some cognitive impairment, we will only consent patients who have been determined to have the capacity to give consent. This determination will be made by [name], [name] Im or [name] who are specialists in Brain Injury and will screen patients to determine if they are in a stable cognitive state, whose capacity to give consent is not expected to fluctuate. Only such patients will be enrolled in the study. We will provide information to the subjects in terms that they can fully understand, and capacity to consent will be determined by the subject's verbal understanding of the protocol as determined by the PI. We will not exert any overt or covert coercion, and no financial incentive will be offered. The consent document that each potential subject will be asked to sign will be written in the language that he or she understands, and will be approved by the IRB.

III. METHODS AND PROCEDURES

1. Methods and Procedures.

Patients will sign informed consent and be required to undergo self-assessment (using the TIRR symptom checklist), caregiver assessment (using the Neurobehavioral Functioning Inventory/NFI), and clinician assessment (using NRS-R) to determine neurobehavioral status on study entry. Screening procedures will also include medical history and interview, review of medications and imaging records to ensure that participants meet inclusion/exclusion criteria. Screening procedures will take place at the Motor Recovery Laboratory. The following outcome measures will be administered at baseline and at the end of the 6-week tDCS intervention.

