Moss Attention Rating Scale (MARS): The Moss Attention Rating Scale (MARS) is a recently developed clinical measure of attention deficits for patients with TBI in the acute inpatient rehabilitation setting (Whyte, Hart et al. 2008). It involves ratings of observed patient behavior by rehabilitation professionals such as nursing staff, occupational therapists, speech therapists etc. The items on the MARS measure deficits in three distinct subcomponents of attention: *restlessness/distractibility*, *sustained/consistent attention*, and *initiation*. *Restlessness/distractibility* is defined as the ability to inhibit preservative, restless, or irrelevant responses (similar to executive attention on the ANT-R), *sustained/consistent attention* is defined as the ability to sustain attention and persist on tasks (similar to alerting on the ANT-R), and *initiation* is defined as the ability to initiate a task without cueing (similar to orienting on the ANT-R). This scale will be completed by the PI or her delegates during the visit.

Sniffin' Stick test: Sniffin' sticks is a nasal chemosensory performance evaluation test using pen like odor dispensing devices which was introduced by Kobal et al. It comprised three subsets namely an odor identification test, an odor discrimination test, and a test for olfactory threshold. The screening 12 test used in our experiment is a smell identification test with 12 different everyday smells. The patients will name the smells using a multiple choice form which offers four definitions for each pen, among which only one choice would be correct. Chemosensory impairments are common after traumatic brain injury occurring in about 20 percent of patients depending on the mechanism of injury. This test can be used to estimate whether a TBI subject has normal or reduced olfactory capacity and also can be used to understand the relationship between olfactory dysfunction and emotional dysregulation.

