1.5 Intervention with active and sham tDCS and computerized cognitive re-training

After providing informed consent approved by the IRB of New York University School of Medicine (NYUSoM), all patients will undergo testing with the above listed outcome measures. They will then be randomized into the two intervention groups, the groups being (1) tDCS + cognitive re-training, and (2) sham tDCS + cognitive re-training. The intervention will be carried out for 20 minutes twice a week for 6 weeks during which the subjects in each group will be engaged in re-training using visual cognitive re-training software programs for 30-45 minutes during each session (www.positscience.com). These re-training programs have been used in patients with TBI and have been shown to be effective (Fisk, Novack et al. 2002; Calvanio, Williams et al. 2004; Novack, Banos et al. 2006). Cognitive re-training will thus be individualized to each patient's cognitive level, but still be systematic, and will not need direct one-on-one supervision by a neuropsychologist.

Transcranial direct current stimulation will be delivered by trained study personnel using the saline-soaked pair of surface sponge electrodes (35 cm²) delivered by a specially developed, battery-driven, constant direct current stimulator (Fisher Wallace Cranial Stimulator, Fisher Wallace Laboratories, New York) with a maximum output of 4 mA (**Fig. 1**). FDA approval: The Cranial Stimulator is an FDA cleared device indicated for application of electrical stimulation to a patient's head to treat insomnia, depression, or anxiety. TBI subjects experience insomnia, depression and anxiety and all subjects enrolled in this study will have some combination of these problems. The purpose of this study is to understand the mechanisms behind the depression, anxiety and insomnia that patients with TBI experience. The hypothesis is that emotional dysregulation contributes to the symptoms. This device will therefore be used in alignment with FDA clearance indications. To stimulate the DLPFC, the anode electrode will be placed over F3 according to the 10-20 international system for EEG electrode placement (Fregni, Boggio et al. 2005) (**Fig.2**). The cathode will be placed over the contralateral supraorbital area.

Fig.1. FDA approved Fisher Wallace Cranial Stimulator.

[figure not shown]

Fig.2. Placement of electrodes (Rosa and Lisanby 2012).

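### The one person declared unblinded, the PI, may complete the observer-rated Moss scale after treatment, and masking of the stimulator operators is not described

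*Protocol*

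**What the plan says.** Section I.3 (Study Design) sets the masking rule: "Subjects and study personnel performing assessments and data analysis will be blind to group assignment. Only the PI will be unblinded". The same paragraph says "Randomization will be carried out by the PI", by coin flip, so the PI knows every assignment.

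Section III.1.1 describes the MARS as "ratings of observed patient behavior by rehabilitation professionals" and then says "This scale will be completed by the PI or her delegates during the visit". The MARS is one of the measures introduced in section III.1 by "The following outcome measures will be administered at baseline and at the end of the 6-week tDCS intervention". Section I.3 confirms that after treatment "the subjects will then be re-tested on the baseline assessments and resting state MRI", at visits 17 to 20.

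Three other places bear on who rates and who knows the arm:

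- Section III.1.5 gives delivery of stimulation to trained study staff. Sham consists of turning the stimulator off after 5 seconds, and the procedure is described as blinding patients.
- Section III.2 (Data Monitoring) promises independent assessors for outcomes without saying who they are.
- Section V makes the original PI and her delegates responsible, as one group, for assessments, the tDCS intervention and data analysis.

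**The concern.** Aim 2 is a comparison of active with sham stimulation. On a scale that depends on the rater's judgement, a rater who knows the arm can produce a difference that reflects expectation and not tDCS. The protocol sees this, since it requires blind assessors, but it then names the only unblinded person as an allowed rater.

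The MARS could reach the treatment comparison. Section III.2 names it only for correlation with the ANT-R under Aim 1. However, the Aim 2 repeated-measures ANOVA is to cover measures of executive attention, and section III.1.1 likens the MARS restlessness/distractibility component to exactly that: "irrelevant responses (similar to executive attention on the ANT-R". Section III.2 also says the ANOVA will supply the data for sizing later trials, so a biased difference on an included measure would be carried into their design.

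**Working it through.** **Step 1: set the passages side by side.**

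| Question | Protocol text | Consequence |
|---|---|---|
| Who must be blind? | I.3: assessors and analysts | Includes whoever rates the MARS |
| Who is unblinded? | I.3: the PI, who randomizes | The PI knows every arm |
| Who may rate the MARS? | III.1.1: the PI or her delegates | The PI is allowed |
| When is it rated? | III.1 and I.3: baseline and after treatment | Includes visits 17–20 |
| Is baseline affected? | III.1.5: after baseline testing, "They will then be randomized into the two intervention groups" | No; the arm does not yet exist |
| Do independent assessors settle it? | III.2: general promise, no roles named | No; III.1.1 and V still stand |

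The conflict is therefore limited to post-treatment ratings. Unblinded rating is permitted, not certain: a blind delegate could do every one of them and no sentence would be breached.

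**Step 2: operators.** Read literally, I.3 makes operators blind, because only the PI is unblinded. But whoever turns the device off after 5 seconds knows that the session is sham. Unless the PI alone does this, or operators are masked in a way the protocol does not describe, those operators learn the arm. Section V does not keep them apart from the raters.

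**Step 3: illustrative size.** The protocol gives no figure to reproduce and no bias size. Inputs:

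- n = 10 per arm (I.3 and III.2).
- No true effect; two-sided 5% test (assumed).
- Rater bias of 0.5 SD (assumed), read as a difference between arms, since an equal shift in both arms cancels.
- Pre–post correlation r = .44 to .67. These are the two-week Trails B retest values in III.1.1, used as a proxy because none is given for the MARS.

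The group-by-time interaction in a 2 × 2 design equals a two-sample t test on change scores. In units of the outcome SD:

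- SD of change = √(2(1 − r)): 1.058 at r = .44 and 0.812 at r = .67.
- Average bias b = share of ratings unblinded × 0.5.
- Noncentrality = b / √(2(1 − r)) × √(n/2), with 2n − 2 = 18 degrees of freedom and critical value 2.101.
- Example, all unblinded: 0.5/1.058 × √5 = 1.056 and 0.5/0.812 × √5 = 1.376.

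| Share unblinded | b (SD) | False-positive rate, r = .44 | r = .67 |
|---|---|---|---|
| All | 0.5 | 0.170 | 0.256 |
| Half | 0.25 | 0.079 | 0.100 |
| A quarter | 0.125 | 0.057 | 0.062 |
| None | 0 | 0.050 | 0.050 |

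A simulation of 200,000 runs, with the unblinded ratings drawn at random, agreed closely: all 0.168 and 0.256; half 0.077 and 0.098; a quarter 0.057 and 0.062; none 0.049 and 0.050.

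**Step 4: sensitivity to n.** Sections I.3 and II.1 also give 40 TBI subjects. At 20 per arm (38 degrees of freedom) the noncentrality with all ratings unblinded is 1.494 to 1.946, and the rate rises to about 31–47%. A fixed bias becomes more likely to reach significance as the trial grows.

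**The case against.** The best reply is that the passages can be read together. I.3 lays down the rule, the independent-assessor promise in III.2 supports it, and the permission in III.1.1 is an either/or that also covers baseline. The PI could rate at baseline and a blind delegate after treatment. That is right, and it is why the finding is a permission and not a planned unblinded rating. It does not remove the problem, because nothing in the text tells the PI not to rate after treatment.

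Second, the reach is narrow. The MARS is named only for an Aim 1 correlation, and its place in the Aim 2 ANOVA is an inference from a likeness drawn for one of its three components. The ANT-R is computerized, the TAS is self-reported, and physiological recordings and MRI leave little room for rater expectation. This stands and limits the stakes. Facial coding is blinded in III.2, but to diagnosis, with nothing said there about treatment arm.

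Third, the operator point is secondary. Blindness of operators is implied, and the overlap between operators and raters comes from a staffing paragraph and not a procedure. This is fair: taken alone, it would be little more than missing detail. It matters because the same pool of people may also rate.

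Fourth, the percentages rest on an assumed bias and a proxy correlation. They show scale only; the contradiction does not depend on them.

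**Conclusion.** The concern holds. The protocol requires blind assessors, names the randomizing PI as the only unblinded person, and then allows the PI to make a judgement-based rating after treatment. The independent-assessor statement withdraws neither III.1.1 nor section V. Baseline ratings are unaffected, and the objective, computerized and self-reported measures are little exposed.

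The actual size cannot be known from the protocol. It depends on how many post-treatment ratings the PI or an unmasked operator makes, on the size of any bias, and on whether the MARS enters the Aim 2 analysis; the range in the working runs from no inflation to a severalfold one. This should be fixed, but it is not fatal to the pilot.

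**What to change.** 1. **Section III.1.1:** remove the PI as a rater of the MARS at post-intervention visits. Require that the MARS and any other tester-rated outcome at visits 17–20 be done by delegates who do not know the arm and have not operated the stimulator for that subject.
2. **Section I.3:** either list the device operators as unblinded or state how they are masked.
3. **Sections III.2 and V:** identify the independent assessors as these delegates, and state that for each subject stimulation and post-intervention rating are done by different people. Section V should also be squared with the blind-analysis rule in I.3, since it assigns analysis to the PI and delegates as well.

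The cost is wording in four places and a duty roster. No subjects, visits or measurements are added. The drawback is a small scheduling constraint: an operator cannot rate the same subject after treatment. The protocol already provides for delegates but gives no staff count, so the team should confirm that there are enough to separate the two tasks.

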1.1 NeuroCognitive Testing

Neurocognitive Domains	Neurocognitive Measures
Premorbid Functioning	Wechsler Test of Adult Reading (Wechsler 2001) n = 60, a = .95 Time = 10 min
Attention/Working Memory	Trails A (Reitan and Wolfson 1985) n = 25, a = .73 Time = 3 min WAIS Subtest: Digit Span (Wechsler 2008) n ~ 16, a = .94 Time = 4 min Auditory Consonant Trigrams (Peterson and Peterson 1959) n = 20, a = .85 Time = 10 min
Executive Function	Trails B (Reitan and Wolfson 1985) n = 25, a = .87 Time = 5 min Stroop Color-Word (Golden 1978) n ~ 300, a = .83-.91 Time = 5 min
Information Processing Speed	Symbol Digit Modalities Test (Smith 1993) n ~ 110, a = .80 Time = 5 min

n = # items; a = alpha; Time = time to administer

Premorbid Neurocognitive Functioning:

Wechsler Test of Adult Reading (Wechsler 2001). The WTAR estimates pre-morbid intellectual functioning for adults (16-89 years old). Thus, it allows for the identification of relative impairments by detecting discrepancies between levels of premorbid functioning and current functioning. This is particularly important for detecting impairment in higher functioning individuals, who may currently have average performance where they performed in the superior range premorbidly.

Attention/Working Memory:

Trails A (Reitan and Wolfson 1985) is a test of attention and complex visual scanning with a psychomotor speed component. Trails A requires individuals to connect randomly arranged numbers sequentially from lowest to highest number. Like many attention and motor speed measures, Trails A is sensitive to cognitive decline.

Digit Span (Tulsky, Zhu et al. 1997) requires the respondent to recall digits forward and backward and is used to measure working memory. Although forward span usually remains stable and resistant to brain disorders (Lezak, Howieson et al. 2004), individuals with diffuse

damage (e.g., mild TBI) can have mental tracking difficulties and those with more severe TBI can perseverate from previous items (Ruff, Evans et al. 1986). However, backward span is more sensitive to brain disorders, particularly diffuse damage which is characteristic of TBI (Fork, Bartels et al. 2005).

Auditory Consonant Trigrams (Peterson and Peterson 1959) is a test of information processing and divided attention. Three consonants are presented to the individual, who must remember them after intervals of 0, 9, 18 and 36 seconds. During intervals, the person is required to count backwards aloud by threes from different starting points. The task captures everyday experience of momentary distraction and subsequent loss of recently learned information and can identify dysfunction following mild neurological changes (Boone 1999).

Executive Function:

Stroop Color-Word Test (Golden 1978) is a measure of selective attention, verbal processing speed, cognitive flexibility and response inhibition. Poor performance on the Stroop has been found to be associated with frontal systems dysfunction secondary to closed head injury (Trenerry, Crosson et al. 1989). The test is a good discriminator between individuals with TBI and controls (Asikainen, Nybo et al. 1999; Bate, Mathias et al. 2001; Wallesch, Curio et al. 2001).

Trails B (Reitan and Wolfson 1985) is a speeded test of attention, sequencing, mental flexibility, visual search and psychomotor speed. The participant draws lines connecting alternating circles with numbers and letters in sequence. Speed of performance on Trails B is considered to be vulnerable to the subtle cognitive effects of TBI (Lezak 1995; Rasmusson, Carson et al. 1996). Test-retest reliability over two weeks was reported as .44 in a non-disabled sample and .67 in people with disabilities. Trails B errors are considered valid measures of dorsolateral prefrontal dysfunction (Stuss and Levine 2002).

Information Processing Speed:

Symbol Digit Modalities Test (Smith 1993) is used to measure visual scanning, tracking and motor speed, and it is sensitive to subtle cognitive impairment. A score below 1.5 standard deviations below the mean is indicative of cerebral dysfunction. Performance declines are observed with increasing age, demonstrating that cognitive changes could be detected with this measure. This test is sensitive to brain injury (Lezak 1995; Spreen and Strauss 1998).

Attention Network Test-Revised (ANT-R): The ANT-R is a computerized half-hour test that provides a measure of the efficiency of the attentional networks involved in *alerting, orienting and executive attention*, three aspects of attention that have been shown to activate anatomically distinct networks in the brain and are differentially innervated by neuromodulatory systems (Fan, McCandliss et al. 2005). The components of attention described by the ANT encompass the clinical modules such as focused, sustained, selective, alternating, and divided attention (Sohlberg and Mateer 1989), but are better suited to understand the underlying mechanisms.

Alerting describes the function of tonically maintaining the alert state and physically responding to a warning signal (similar to sustained attention or vigilance), and activates thalamo-cortical networks involving anterior and posterior cortical sites. Efficiency of the alerting network is

examined by changes in reaction time (RT) resulting from a warning signal. **Automatic and voluntary orienting** are involved in the selection of information among multiple sensory inputs (similar to focused attention), and activate the parietal cortex and frontal eye fields. Efficiency of orienting is examined by changes in RT that accompany cues indicating where the target will occur. **Executive attention** describes a set of more complex operations that include detecting and resolving conflicts in order to control thoughts or behaviors (encompasses selective, alternating and divided attention), and activates the anterior cingulate along with several other brain areas. The efficiency of the executive network is examined by requiring the subject to respond by pressing two keys indicating the direction (left or right) of a central arrow surrounded by congruent, incongruent or neutral flankers. However, the three networks are also integrated and interact during functional tasks (Fan, Gu et al. 2009).

Moss Attention Rating Scale (MARS): The Moss Attention Rating Scale (MARS) is a recently developed clinical measure of attention deficits for patients with TBI in the acute inpatient rehabilitation setting (Whyte, Hart et al. 2008). It involves ratings of observed patient behavior by rehabilitation professionals such as nursing staff, occupational therapists, speech therapists etc. The items on the MARS measure deficits in three distinct subcomponents of attention: *restlessness/distractibility*, *sustained/consistent attention*, and *initiation*. *Restlessness/distractibility* is defined as the ability to inhibit preservative, restless, or irrelevant responses (similar to executive attention on the ANT-R), *sustained/consistent attention* is defined as the ability to sustain attention and persist on tasks (similar to alerting on the ANT-R), and *initiation* is defined as the ability to initiate a task without cueing (similar to orienting on the ANT-R). This scale will be completed by the PI or her delegates during the visit.

Sniffin' Stick test: Sniffin' sticks is a nasal chemosensory performance evaluation test using pen like odor dispensing devices which was introduced by Kobal et al. It comprised three subsets namely an odor identification test, an odor discrimination test, and a test for olfactory threshold. The screening 12 test used in our experiment is a smell identification test with 12 different everyday smells. The patients will name the smells using a multiple choice form which offers four definitions for each pen, among which only one choice would be correct. Chemosensory impairments are common after traumatic brain injury occurring in about 20 percent of patients depending on the mechanism of injury. This test can be used to estimate whether a TBI subject has normal or reduced olfactory capacity and also can be used to understand the relationship between olfactory dysfunction and emotional dysregulation.

King-Devick Test: King-Devick test is an objective way of measuring visual tracking and saccadic eye movements. It is based on the identification of impaired eye movements and saccades which indicates a suboptimal brain function. The subjects are asked to read out the numbers aloud on three different cards from left to right as quickly as possible without making any errors. The final score is the sum of the three test card scores. The charts become progressively difficult from the first to the third. It can be used as a good visual screening test in addition to other test in patients with traumatic brain injury. Deficiency of saccadic eye movements can be an indicator of mild traumatic brain injury or concussion injury.

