- 2) **Emotional recognition:** Responses to emotion recognition questions, using both the reactivity film clips described above and picture stimuli will be recorded and coded; coded data from patients and controls will be compared.
- 3) **Emotional regulation with disgust videos:** For the three conditions, physiological responses (as described above) will be recorded, and input from baseline will be subtracted from input across the most intense segment of the clip. Facial behavior will be recorded and coded. Data from patients and controls will be compared.

For coding facial behavior, coders will be blind to the diagnostic status of the participant and code videos with sound muted; coding will be assessed for inter-rater reliability

Pearson's correlation analysis will be performed to examine the relationship between reaction time (RT) scores indicating alerting, orienting and executive attention on the ANT-R and emotional recognition, reactivity and regulation scores. Differences in patients and controls will be computed. We will also correlate the clinical scores on the MARS with the ANT-R and the TAS-20 scores with the emotional battery scores. We expect that deficits in selective or executive attention will be related to deficits in emotional appraisal in the patients.

2) To determine whether anodal tDCS applied over the dorsolateral prefrontal cortex in conjunction with computer assisted cognitive re-training of attention will lead to greater improvement in attention and/or emotional regulation compared with sham-tDCS + cognitive re-training. Hypothesis: Patients receiving tDCS + cognitive re-training will show greater improvement in post-intervention measures of attention and emotional regulation.

A 2 (condition) x 2 (pre and post session) repeated measures ANOVA with a priori orthogonal contrasts will be performed on the variables related to executive attention and emotional appraisal to determine whether there is a difference both within and between groups. This analysis will also provide data for power analysis to determine the sample size for subsequent interventional studies. We expect that patients receiving tDCS + cognitive re-training will show greater improvement in post-intervention measures of attention and emotional regulation.

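### Aim 1 names only unadjusted patient-control comparisons and simple correlations, although the protocol collects the WTAR so that impairment can be judged against premorbid level

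*Protocol*

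**What the plan says.** Protocol section III.1.1 (NeuroCognitive Testing) opens its table with the premorbid measure: "Wechsler Test of Adult Reading (Wechsler 2001) n = 60, a = .95 Time = 10 min". The text below the table explains it: "The WTAR estimates pre-morbid intellectual functioning for adults (16-89 years old"), and "it allows for the identification of relative impairments by detecting discrepancies between levels of premorbid functioning and current functioning". The section adds that this matters most for people of high ability, whose present score may be average although it was superior before the injury.

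The Aim 1 part of section III.2 (Data Analysis) compares patients with controls on coded and baseline-subtracted emotion scores. It then turns to attention: "Pearson's correlation analysis will be performed to examine the relationship between reaction time (RT) scores indicating alerting, orienting and executive attention on the ANT-R" and the emotion scores. It continues: "Differences in patients and controls will be computed". Neither the WTAR nor any other covariate is named, and there is no discrepancy score or partial correlation.

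On timing, section III.1 introduces the whole battery with "The following outcome measures will be administered at baseline and at the end of the 6-week tDCS intervention". Section I.3 (Study Design) says "After completion of treatment, the subjects will then be re-tested on the baseline assessments and resting state MRI", and for the other group "Healthy Control Subjects will have a total of three testing visits (1-3) only". Neither section makes an exception for the WTAR.

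**The concern.** Aim 1 is an observational comparison. Its hypothesis is that patients are impaired relative to controls and that executive-attention deficits go with deficits in emotional appraisal. Section II (Characteristics of the Research Population) describes no matching of controls on premorbid ability, education or age, and ages run from 18 to 85. If the groups differed in ability before injury, a plain difference in means mixes that gap with the effect of injury. If premorbid ability influences both an attention score and an emotion score, the two will correlate among patients even where injury has created no link between them.

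The protocol recognises the first problem in its reason for giving the WTAR, and the WTAR is the only listed measure of premorbid level. The analysis text then leaves it unused. The pilot data are also meant to inform the size of later studies, so a distorted contrast could be carried forward.

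A smaller matter is the retest. A measure that by its own description estimates function before injury has nothing to register after six weeks of treatment. Repeating it also produces a second premorbid value with no rule for choosing between the two.

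**Working it through.** The plan states no figure on this point, so there is none to reproduce. The check has a textual part and an illustration of scale.

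**Where the WTAR appears.**
- Section III.1.1: listed and described, with a stated purpose.
- Section III.1 and section I.3: covered by the general retest instructions.
- Section III.2, Aim 1: not named.
- Section III.2, Aim 2: not named. The repeated measures ANOVA is limited to variables of executive attention and emotional appraisal, and the WTAR is classed under premorbid functioning.
- Section III.2, Aim 3: imaging only.

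Controls attend visits 1 to 3, which include the baseline neuropsychological assessments. A baseline WTAR value should therefore exist in both groups.

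**Inputs for scale.**
- From the protocol (section II.1): 40 patients and 25 controls.
- Assumed, not in the documents: premorbid gap g = 0.25 to 0.5 SD, and correlation r = 0.1 to 0.5 between the WTAR and an Aim 1 score.

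**Group difference.** In SD units, the standard error is √(1/40 + 1/25) = √0.065 = 0.255. The shift from leaving out the WTAR is r × g. The last column is the rejection rate of a nominal two-sided 5% test when injury has no effect (normal approximation).

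| r | g | Shift (SD) | Shift / SE | Rejection rate |
|---|---|---|---|---|
| 0.1 | 0.25 | 0.025 | 0.10 | 5.1% |
| 0.1 | 0.50 | 0.050 | 0.20 | 5.4% |
| 0.3 | 0.25 | 0.075 | 0.29 | 6.0% |
| 0.3 | 0.50 | 0.150 | 0.59 | 9.1% |
| 0.5 | 0.25 | 0.125 | 0.49 | 7.8% |
| 0.5 | 0.50 | 0.250 | 0.98 | 16.5% |

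Sections I.3 and III.2 also speak of two randomised groups of 10. If only 20 patients were available, the standard error would be √(1/20 + 1/25) = 0.30 and the largest shift would be 0.25 / 0.30 = 0.83 standard errors.

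**Correlation among 40 patients.** If the WTAR correlates r with both scores and nothing else links them, the induced correlation is r². On Fisher's z scale the standard error is 1/√(40 − 3) = 0.164.
- r = 0.1: induced correlation 0.01, rejection rate 5.0%
- r = 0.3: induced correlation 0.09, rejection rate 8.5%
- r = 0.5: induced correlation 0.25, rejection rate 34%

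At the low end the effect is negligible. At the high end it is about one standard error for the group difference, and for the correlation it is a marked excess of false positives.

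**The case against.** The strongest reply is that this is silence and not error. Covariates are commonly left to a statistical analysis plan, which is not shown, and no sentence in the protocol forbids using the WTAR. Trails, Stroop, Digit Span and the other paper tests are not named in the analysis section either. This stands as far as it goes: the protocol does not contradict itself, and the missing covariate alone would not be a finding. But the protocol does name a method for Aim 1, a simple Pearson correlation and comparisons without adjustment, for a non-randomised contrast. The WTAR also differs from the other unnamed tests, because its written purpose is to interpret them.

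A second reply is that many Aim 1 scores are already referenced to the same person. The alerting and orienting scores of the ANT-R are changes in reaction time, and the physiological scores have baseline subtracted. General ability may enter such scores only weakly. This also stands, and it is why the assumed correlation starts at 0.1.

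A third is that reading may itself have been lowered by injury, so that adjustment removes part of the effect sought. That argues for showing both results, and against replacing one with the other.

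A reader might also infer from the list of outcome measures that the WTAR is analysed as a treatment outcome and that Aim 2 suffers. The documents do not support this, because the Aim 2 ANOVA does not include it.

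**Conclusion.** The point holds as a modest one. The protocol collects a measure in order to judge impairment against premorbid level, and then specifies an Aim 1 analysis that does not use it, in groups not described as matched. Confounding by premorbid ability is possible in both the group comparisons and the attention-emotion correlations.

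How large it is cannot be known from the documents. The range of 0.025 to 0.25 SD, against a standard error of 0.255 SD, rests wholly on the assumed gap and correlation. The induced correlation of 0.01 to 0.25 further assumes that the WTAR relates equally to both scores. It would be too strong to say that Aim 1 is biased by a known amount, or that the adjusted analysis is the only correct one.

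The retest is a matter of labelling and of 10 minutes of testing per patient. It affects no treatment comparison.

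**What to change.** In section III.2, Aim 1, add that each patient-control comparison of attention, emotion-recognition and emotion-regulation scores will also be reported with baseline WTAR as a covariate. Each attention-emotion correlation should likewise be reported as a partial correlation given baseline WTAR. Both go beside the unadjusted results, with a sentence noting that adjustment may remove part of a true effect if injury lowered reading.

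In sections I.3, III.1 and III.1.1, mark the WTAR as a baseline-only measure and drop it from the post-treatment battery.

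The cost is a few sentences and one degree of freedom per adjusted analysis. No new data are needed, and each patient is spared a 10-minute test at retest.
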